Date: February 20, 2017
Version Number: 11
Principal Investigator: [name]
Application Number: 1212915
Application Title:

Does Optimized General Anesthesia Care Reduce Postoperative Delirium In Older Patients Undergoing Hip Fracture Repair?

Protocol

1. Abstract

The overall objective of this proposal is to determine if optimized general anesthesia care of elderly patients undergoing hip fracture surgery will minimize postoperative delirium (POD) and improve postoperative outcomes. A proactive geriatric consultation using a multifactorial bundle of pharmacological and non-pharmacological strategies in the perioperative period has been shown to effectively reduce POD, but even with these perioperative medical interventions, more than 30% of patients undergoing hip fracture surgery experience POD.^{1,2}

There is tantalizing preliminary evidence suggesting that intraoperative interventions may also have the potential to further decrease POD.³⁻⁶ This prospective randomized clinical trial (RCT) will focus on the intraoperative optimization of: 1. blood pressure, 2. depth of anesthesia, 3. cerebral oxygenation, and 4. postoperative pain management in an effort to further reduce POD. All of these interventions can easily be managed by anesthesia providers during surgery. A total of 160 patients will be randomized to optimal versus usual anesthesia care for hip fracture surgery to determine the impact of this targeted anesthesia care bundle on the severity and incidence of POD. The results of our proposed study are intended to enhance patient safety by developing a relatively easily implemented, generalizable anesthesia management strategy that can be used by anesthesia providers in both academic and private settings. This proposal has the potential to further reduce POD, thereby decreasing patient morbidity and mortality.

2. Objectives (include all primary and secondary objectives)

The primary objective of this proposal is to develop an optimized general anesthetic plan, focusing on anesthetic depth, blood pressure control, and cerebral oxygenation for elders undergoing hip fracture surgery. This protocol will compare usual care to optimal general anesthesia care to test the following hypotheses:

The use of an optimized general anesthetic technique for elders undergoing hip fracture surgery will:

- **Primary hypothesis: decrease the severity of POD**
- **Secondary hypothesis 1: decrease the incidence and duration of POD**

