At the present time, only multi-component medical interventions have shown to consistently reduce POD.^{1,12,13} Although it makes sense that neuraxial anesthesia would be associated with less POD than general anesthesia (GA), there is no evidence to support this theory, possibly because sedation levels were not controlled in these studies.¹⁴ There is, however, limited evidence that minimizing anesthetic exposure during hip fracture surgery might decrease POD. Sieber et al.³ randomized elderly patients undergoing hip fracture repair with spinal anesthesia to light versus deep propofol sedation for the procedure and found that light propofol sedation (BIS > 80) decreased the incidence of POD by 50% compared with deep sedation (BIS =50). Despite the promising results of this study, the study results have been questioned because the two treatment groups were not matched with respect to cognitive and functional status.¹² A more important issue is that spinal anesthesia is rarely used for patients undergoing hip fracture surgery. A large retrospective study of 56,729 patients having hip fracture surgery in the US found that only 28% of patients received regional anesthesia and that GA was much more common (72%).¹⁵ There are a multitude of reasons that anesthesia providers prefer to administer GA for hip fracture surgery including patient preference, avoidance of pain during positioning of the patient, difficulty with block placement in elderly patients with arthritic spines, and the use of anticoagulation in many elders. An optimized general anesthetic technique is, therefore, needed to improve postoperative outcomes in elders receiving GA for this hip fracture surgery.

Modifiable Intraoperative Factors

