There is growing evidence that limiting the amount of anesthesia during GA may decrease the incidence of POD. Chan et al.⁵ prospectively randomized elderly patients undergoing elective major surgery to either BIS-guided or routine care anesthesia and found that patients in the BIS-guided group received less anesthetic and had a 35% decrease in the incidence of POD. A second prospective study randomized elders undergoing elective surgery and found that intraoperative monitoring with BIS was associated with a lower incidence of delirium, “possibly by reducing extreme low BIS values.”⁶ In a third study, a retrospective analysis of patients undergoing general anesthesia found a trend toward less POD with BIS-guided compared to end-tidal anesthetic concentration guided protocols.¹⁶

Near-infrared spectroscopy (NIRS) can be used to monitor the balance between cerebral oxygen delivery and consumption.¹⁷ There is moderate to close correlation between regional cerebral oxygen saturation (rScO₂) and mixed venous saturation (SvO₂) in awake and anesthetized patients, indicating that rScO₂ is reflective of not only cerebral, but also systemic oxygen balance.^{18,19} A longitudinal study of healthy elderly patients undergoing abdominal surgery found that intraoperative cerebral desaturations occurred in 25% of patients and was associated with a higher incidence of early postoperative cognitive decline and longer hospital stays.²⁰ Murkin et al.⁷ randomized 200 patients undergoing coronary artery bypass to either NIRS monitoring with active treatment of cerebral desaturations or usual care and found that active treatment significantly decreased mortality and major organ morbidity (stroke, myocardial infarction, ventilation > 48 hours). There are no studies evaluating outcomes with the use of NIRS monitoring with a predetermined treatment protocol on outcomes after noncardiac surgery.

There is conflicting literature as to the relationship between intraoperative hypotension and POD.^{21,22} A recent abstract found that nearly half of elderly patients had intraoperative mean arterial BP (MAP) decreases of 20% or more from baseline.²² While these investigators did not find a relationship between intraoperative hypotension and POD, their findings suggest that intraoperative blood pressure variance may have an impact on the occurrence of POD.

4. Study Procedures

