Data for the treatment group (OP Care) will be analyzed after the first 5 patients and then after each additional 15 patients are treated to ensure compliance with the treatment protocol (BP and BIS in recommended range). Patients will be followed daily during the hospitalization and charts reviewed to determine transfusion requirements and prevalence and types of postoperative complications.

Power Analysis: The primary hypothesis states that optimized anesthesia care will decrease the severity of POD compared to usual care. We expect that the severity score in the optimized group will be 14 ± 3 versus 18 ± 4 in the usual care group similar to that seen in previous treatment studies.³⁵ To have 80% power to detect such a difference when testing a two sided alternative and alpha of 0.05 will require 22 subjects per group. This is the number of subjects that qualify as confused. Only patients with POD contribute to the DRS severity sample, so if 30% of subjects are expected to experience delirium, then the total sample size for the study would have to be $44/.3 = 148$, or 74 per group. We plan to enroll 80 patients per group for a total sample size of 160.

Interim Analysis: There will be no interim analyses and no safety monitoring board so there are no early stopping rules.

Data management

The data collected on the data collection forms developed for this study, will be obtained specifically for research purposes. Research data will be stored in a locked research office in the Department of Anesthesiology at the University Hospital. All patient identifiable information will be stored in a locked file cabinet in this locked research office or stored on a secure server in this locked office. Only research personnel listed on the IRB proposal will know the log in and password information for this server. The demographic, hemodynamic, laboratory and historical data that are collected at the time of the intraoperative study are part of the routine medical record documenting the patient's care in the perioperative period. The patient's identity will be specifically protected and confidentiality will be maintained in any publication of data.

8. Risks

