This study will enroll 160 patients scheduled for surgery for repair of a hip fracture. All subjects will have an injury requiring surgery and general anesthesia is routinely used at the University of Missouri-Columbia for repair of a hip fracture. The anesthesia used in the protocol is routine care and does not add additional risk to the patients. In the optimized care group, we will apply two additional monitors, a cerebral oximeter and a depth of anesthesia monitor. Both of these monitors are non-invasive and FDA approved for use in the operating room so the additional risk of using these monitors is minimal. Both devices use a bandage-like sensor applied to the forehead. There are no reports of allergies or rashes from these sensors.

The Hip Fracture Improvement Team evaluates all patients who are admitted to the University Hospital with this type of injury and they will evaluate all of the patients in the study and adhere to the Hip Fracture Management Protocol in the perioperative period. Thus, the perioperative care of the patient will be unchanged for patients enrolled in this study.

Elderly patients with hip fractures may have cognitive impairment and ensuring informed consent can be a challenge in this type of patients. Patients will not be enrolled in the study if they are delirious when approached and will be excluded from the study if they exhibit significant cognitive impairment as evidenced by a score < 18 on the baseline MMSE. However, inclusion of older adults with cognitive impairment in research studies is necessary because preoperative cognitive impairment is one of the primary risk factors for POD.^{32,31} We will request IRB approval to obtain consent from a legally authorized representative (as outlined in a Missouri statute) if a subject's decision-making capacities are in question. If the subject agrees to the research protocol, but we are unsure of his/her ability to fully understand the research, we will obtain additional informed consent from a family member or legal representative.

The baseline cognitive and functional tests and questionnaires are brief and are not adverse. These tests, however, can be frustrating for older subjects. To prevent this problem, the test battery is limited to approximately 15 min and we will ask the subject if he/she needs a break during testing. We will also have

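### Section 7 turns 22 delirious patients per group into 80 enrolled per group with one 30% rate for both arms, although the trial hypothesises a lower rate under OP care; the OP count is overstated, but power at the stated effect is not lost

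*Combined protocol and SAP*

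**What the plan says.** Section 7, Power Analysis, sets the severity inputs: "We expect that the severity score in the optimized group will be 14 ± 3 versus 18 ± 4 in the usual care group". The target is "To have 80% power to detect such a difference" and the result is "when testing a two sided alternative and alpha of 0.05 will require 22 subjects per group". The section then explains that only patients who develop POD enter the severity comparison, and continues: "so if 30% of subjects are expected to experience delirium, then the total sample size for the study would have to be" 44/.3, reported as 148 in total and 74 per group. Planned enrolment is 80 per group, 160 in total.

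That 30% is not split by arm, and no arm-specific rate appears elsewhere. Four other places bear on it:

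- Section 2, secondary hypothesis 1: OP care will "decrease the incidence and duration of POD".
- Section 1: over 30% of hip fracture patients still develop POD with existing perioperative interventions. Section 3 reports a range of 35 to 65%.
- Section 3: BIS-guided patients in one trial "had a 35% decrease in the incidence of POD", and light sedation in another "decreased the incidence of POD by 50% compared with deep sedation".
- Section 7, Statistical Analysis: severity will be compared with the Wilcoxon rank sum test.

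**The concern.** Dividing 44 by 0.30 yields 22 delirious patients in each arm only if both arms have a 30% delirium rate. Section 1 presents the figure of over 30% as what remains under existing care, so the 30% reads most naturally as a rate before any OP effect. The trial then hypothesises that OP care reduces it.

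Because the primary comparison uses delirious patients only, a treatment that prevents delirium also shrinks the OP side of that comparison. The plan's stated analysis set, 22 v 22, is therefore not what the design is expected to yield in the scenario the trial hopes for. At stake is whether the size, balance and precision of the primary comparison are stated correctly, and whether a shortfall against 22 costs the trial its power.

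**Working it through.** **Inputs from the plan.** 22 delirious per group, 30% rate, 80 enrolled per group, means 14 and 18, SDs 3 and 4 (± read as SD), two-sided alpha 0.05, power 80%: all Section 7. The 35% and 50% relative reductions: Section 3, used here only as illustrative assumptions for OP care.

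**1. The plan's enrolment figure.** 22/0.30 = 73.3, rounded up to 74 per group, 148 in total (44/0.30 itself is 146.7). It reproduces, on equal rates. At 80 per group the expected count is 80 × 0.30 = 24 per arm, a cushion of two.

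**2. Break-even.** The OP arm expects 22 at a rate of 22/80 = 27.5%. Against 30% in usual care, that is a relative reduction of 1 − 0.275/0.30 = 8.3%.

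**3. Expected OP counts with 30% in usual care (24 expected there).** Count = 80 × 0.30 × (1 − reduction); probability from Binomial(80, OP rate).

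| Relative reduction | OP rate | Expected OP count | P(OP at least 22) |
|---|---|---|---|
| 0% | 30% | 24.0 | 72.5% |
| 10% | 27% | 21.6 | 50% |
| 20% | 24% | 19.2 | 27% |
| 35% | 19.5% | 15.6 | 5.2% |
| 50% | 15% | 12.0 | 0.3% |

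**4. If 30% is instead the average of the two arms.** Usual-care rate = 0.60/(2 − reduction). A 35% reduction gives 36.4% v 23.6%, or 29.1 v 18.9 patients, and P(OP at least 22) = 24%. A 50% reduction gives 40% v 20%, or 32 v 16. The OP arm is still below 22.

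**5. Other usual-care rates (expected OP count out of 80).**

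| Usual-care rate | 35% reduction | 50% reduction |
|---|---|---|
| 35% | 18.2 | 14.0 |
| 40% | 20.8 | 16.0 |
| 45% | 23.4 | 18.0 |
| 55% | 28.6 | 22.0 |
| 65% | 33.8 | 26.0 |

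An expected 22 needs a usual-care rate of 0.275/0.65 = 42.3% or 0.275/0.50 = 55%.

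**6. Is 22 needed?** Average variance = (9 + 16)/2 = 12.5, so SD = 3.54. Normal formula: n = 2 × (1.960 + 0.842)² × 12.5/4² = 12.3, so 13 per group; the non-central t gives 14. Dividing 14 by the Wilcoxon's relative efficiency gives 15 (3/π) to 17 (0.864). The stated 22 does not reproduce at 80% power; 22 v 22 gives about 96% by Welch.

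**7. Power at the reduced counts.** Standard error = √(9/n_OP + 16/n_UC), difference 4, Welch t:

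- 15.6 v 24: SE = √(0.577 + 0.667) = 1.115; power 94%.
- 12 v 24: SE = √(0.750 + 0.667) = 1.190; power 90%.

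Simulated Wilcoxon power with counts fixed at 15 v 24 and 12 v 24 is 91% and 86%. With binomial counts in both arms it is about 89% to 90% and 83% to 84%.

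**8. Difference detectable with 80% power (Welch).** 3.06 points at 22 v 22, 3.19 at 16 v 24, 3.45 at 12 v 24.

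**The case against.** The strongest reply is that the primary comparison still meets its own target. The plan promises 80% power for 4 points. At 24 v 16 and 24 v 12 it has more than that, and the detectable differences of 3.19 and 3.45 points lie inside the planned 4. This stands. A reader might infer that the trial is underpowered, or that its detectable difference is wider than planned; the documents support neither, because the 22 carries an undeclared reserve.

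The sponsor can also say that no OP reduction is stated. That stands too. The 35% comes from BIS-guided care in elective major surgery. The 50% comes from sedation depth under spinal anesthesia, a result that Section 3 itself says has been questioned. Neither study tested the OP bundle, so the size of the shortfall is conditional. It is also wrong to say that the OP arm cannot reach 22: the chance is small at 30%, and a usual-care rate of about 42% or more restores an expected 22 at a 35% reduction.

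A reader might argue the other way, that the randomised cohort will run below 30% because patients with low MMSE scores are not randomised while Section 8 says "preoperative cognitive impairment is one of the primary risk factors for POD". The documents give no rate for that cohort, so a scenario such as 20%, with power below 80%, has no figure behind it.

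Finally, planning on expected rather than guaranteed counts is normal practice and is not held against the plan. None of this supports a single rate: the step from 74 to 80 covers a relative reduction of only about 8%.

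**Conclusion.** The point holds as an inconsistency in how the sample size is stated. On the plan's own 30%, read as the usual-care rate, an OP effect on incidence larger than 8.3% relative leaves fewer than 22 expected delirious OP patients. Under the illustrative 35% and 50% reductions the expected split is 24 v about 16 and 24 v 12. If 30% is the two-arm average the shortfall is smaller but remains at those reductions.

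It is not a finding of inadequate power. That conclusion rests on the stated severity inputs, with ± read as SD and roughly normal scores. If the 22 was meant to cover a smaller difference or larger SDs than the text gives, the reserve shrinks. At a true difference of about 3 points, where 22 v 22 has 80% power by the normal formula, 15.6 v 24 has about 76% and 12 v 24 about 71%. So the single rate and the unexplained 22 need to be settled together.

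**What to change.** Rewrite the Power Analysis paragraph in Section 7:

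- Replace the single-rate division with a usual-care rate and an OP rate, both labelled as assumptions, and show a range of usual-care rates and relative reductions.
- For each combination, give the expected delirious count per arm, the Wilcoxon power at 14±3 v 18±4, and the severity difference detectable with 80% power.
- Re-derive the 22 from the stated inputs, or state the inputs, method or margin that produced it.
- Remove the implication that enrolling 160 delivers 22 delirious patients per group.

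No extra patients are needed, and enrolment can stay at 80 per group. The cost is one rewritten paragraph and a less favourable stated count for the OP arm.
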